7.5 Study procedures

7.5.1 Study visits

Each study visit (Figure 1) and MRIs should occur as indicated. These time points are approximated. To accommodate for patient scheduling needs or clinical necessity, study visits will be accepted within a +/- 4 week window of the timepoints noted. Biological samples (CSF, whole blood, apheresis sample) should be collected within 4 weeks of the MRI examination as indicated in Figure 1. Blood samples at baseline and 1 year of treatment will be collected concomitantly with CSF samples.

7.5.2 Clinical and functional evaluations:

to be performed every 6 months

1. Comprehensive neurological evaluation
2. Expanded Disability Status Scale (EDSS (*Kurtzke 1983*))
3. Scripps Neurological Rating Scale (NRS (*Sharrack and Hughes 1996*))
4. MS Functional Composite Scale (MSFC (*Cutter, Baier et al. 1999*), which consists of 3 functional tests:
 - a. Paced Auditory Single Digit Addition Test (PASAT) – measure of cognitive skills
 - b. Timed 25 foot walk – measure of ambulation
 - c. 9-hole peg test – measure of fine finger motor movements
5. Symbol Digit Modality Test (*Sepulcre, Vanotti et al. 2006*)
6. Extensive evaluation of strength, balance and gait within the context of a physical therapy (PT) evaluation may be performed if the subject is not too disabled to participate in these evaluations safely and reliably. This optional evaluation will be conducted in the Biomechanics Laboratory of the Rehabilitation Medicine Department, NIH, CC. It will include, but may not be limited to, the following:
 - a. Evaluation of strength and tone
 - b. Evaluation of gait
 - c. Balance assessment

The assessment of strength and spasticity may require the use of surface EMG.

7.5.3 Neuroimaging evaluation:

MRI imaging will consist of combined MRI of the brain and upper cervical spinal cord, which will be performed every 6 months. This MRI will focus on quantitative and volumetric analyses of brain structure and tissue integrity. Inflammatory activity is less prominent in PP-MS as compared to RR-

MS and consequently, the vast majority of PP-MS patients do not have evidence of gross blood-brain barrier (BBB) disruption as measured by contrast-enhancing lesions (CEL). This is confirmed in our experience in this trial thus far, where true CEL are extremely rare at baseline and their incidence is not increased during the treatment phase. Therefore, we will administer contrast only at the first NIH MRI to identify those patients who may have very rare form of inflammatory PP-MS. Clinical judgment will determine if Gd is administered during the remaining 3T brain MRI scans. The total scan time without Gd administration is approximately 60 minutes. With Gd, the scan time increases to 90 minutes. Because more disabled patients have difficulties with long scans and it is paramount for the integrity of quantitative MRI data to avoid patient movement, the elimination of contrast administration from subsequent scans will improve tolerability of MRI procedure and improve MRI data quality without compromising the safety of patients.

7.5.4 Optical coherence tomography (OCT)

To be performed every 12 months

OCT is a new noninvasive high-resolution method that measures the retinal nerve fiber layer (RNFL) thickness. It works by measuring the echo time delay and intensity of back-reflection of light from different structures in the eye. Recent studies have shown that OCT can detect RNFL thinning, possibly due to axon degeneration, within the retinas of patients with MS, regardless of a clinical history of optic neuritis (Kallenbach and Frederiksen 2007). Moreover, RNFL thickness appears associated with global brain atrophy, (manifested by increasing CSF volume) (Gordon-Lipkin, Chodkowski et al. 2007). As discussed, reliable methods of measurement of neurodegeneration in MS are lacking. While a more thorough characterization is needed, evidence to date suggests that OCT may be developed as a novel measure of neuronal/axonal destruction reflective of neurodegeneration in MS with both diagnostic and prognostic potential (*Gordon-Lipkin, Chodkowski et al. 2007, Kallenbach and Frederiksen 2007*).

7.5.5 Transcranial magnetic stimulation (TMS) and Central motor conduction time (CMCT) calculation

May be performed for clinical care.

Neurophysiological testing, can assess the intactness of conduction through the long tracts, such as the corticospinal tract (CST) (*Ravnborg 1996*). Because CST is invariably affected in PP-MS, the use of motor evoked potentials (MEP) may be performed for clinical care. TMS is a non-invasive technique for evaluating the function of central motor pathways. Single pulse TMS is used to determine the motor evoked potential (MEP), the response generated by excitation of cortical neurons and recorded at the target muscle, and is used to calculate the central motor conduction time (CMCT). In MS patients, CNS dysfunction manifests itself in the form of slowed conduction through demyelinated portions of the corticospinal tracts or more severe disruption of conduction as a result of axonal loss or severe demyelination. This results in a prolongation of CMCT or dispersion of the MEP response such as in a conduction block with resultant decrease in MEP amplitude (*Hess, Mills et al. 1987, Schriefer, Hess et al. 1989*). In progressive MS patients, CMCT has been shown to correlate with the presence of new spinal cord lesions on MRI and changes in the leg CMCT (*Kidd, Thompson et al. 1998*). There is other evidence that suggests that progressive MS patients have greater prolongation of the CMCT compared to relapsing-remitting MS, irrespective of MRI lesion load, suggesting that progressive MS has more perturbations of the corticospinal tracts than are radiologically discernible (*Humm, Z'Graggen et al. 2004*).

7.5.6 Immunological and laboratory evaluation

The immunological and laboratory evaluation will include:

1. Diagnostic/clinical blood-work (clinical care/safety): Baseline labs on untreated patients may be collected under this protocol, or our natural history protocols (09-N-0032 or 89-N-0045). CBC, Chemistry panel including liver function tests will be performed every 3 months for the first year of treatment and every 6 months for the second year of treatment as part of the safety measures. Laboratory evaluations that are performed at times when no NIH MRI/clinical visit is scheduled can be performed outside of NIH with results (including normal values) communicated to NIH investigators. Urine analysis (UA) will be performed every 6 months. Pregnancy tests (for females of child-bearing potential) will be collected up to 24h preceding every MRI exam. All safety laboratory evaluations are represented in the clinical trial scheme on Figure 1.
2. Research Blood (up to 60 cc total): Research blood will be obtained approximately every 12 months (2 baseline and 2 treatment samples); this will be aliquoted and stored or used at the time of collection to meet the Biological/Immunological outcomes stated in section 10.
3. CBC: Additional CBC may be performed in coordination with the research blood if a CBC is not already indicated at these timepoints. This information will be collected solely for research purposes.
4. Lumbar puncture (research): Every patient will undergo a lumbar puncture twice during protocol duration: once at baseline (can be diagnostic LP from which 15-20cc of CSF has been obtained for research for total of 25cc of CSF collected in total) and once after 1 year of therapy (month 12). If the participant has undergone lumbar puncture at any time during their participation in the screening protocol and an adequate sample is already available, this may replace the baseline LP at the discretion of the Principle Investigator. From 15-20cc of research specimen, immune cells will be isolated and expanded and the CSF supernatant will be aliquoted and stored. Lumbar puncture procedure last from 30 minutes to 2 hours. The lumbar puncture will usually be done on an inpatient or day hospital floor of the Clinical Center. The procedure may be performed under fluoroscopic guidance by a credentialed neuroradiologist in Diagnostic Radiology, if there is a patient medical or scheduling need to do so. This involves a small amount of ionizing radiation (0.023 rem per LP). This is substantially less than the limits imposed by the guidelines of the NIH Radiation Safety Committee (5.0 rem per year for adults).
5. Pharmacokinetic (PK) studies (research): Random sampling PK studies may be performed from the CSF twice during the duration of the protocol; at the time of LP. The first sample may be collected at baseline, prior to administration of study medication. The second sample may be collected at month 12 (+/- 2 weeks) of therapy, between 1 and 4 hours after idebenone intake (time selected randomly and documented in the research database). For the analysis of free and total idebenone and its metabolites free and total QS-10, total QS-6 and total QS-4, 8 ml CSF will be taken into two different tubes: 1. For the measurement of total idebenone and its metabolites total QS-10, total QS-6 and total QS-4: 0.5ml of CSF will be collected. For the measurement of free idebenone and its metabolite free QS-10 (i.e. active substances): 0.5ml of CSF will be collected. Samples will be put on ice immediately and centrifuged at 4°C at 1500 g for 10 minutes within 30 minutes after sampling. The cell-free aliquots will be separated and stored separately in polypropylene tubes with a minimum of 0.5ml of CSF per tube. Samples will be stored between -70 and -80°C. The CSF will be collected for possible future PK studies

- to be performed by Santhera Pharmaceuticals upon completion of the collection of all trial samples, using a validated LC-MS/MS method (Inovalab, Reinach, Switzerland)
6. Lymphocytapheresis (research): collecting between $2-4 \times 10^9$ peripheral blood mononuclear cells PBMC, will be performed 3 times during trial: once during pre-treatment baseline and after 1 (month 12) and 2 (month 24) years of treatment. This procedure is performed solely for research purposes. If the participant has undergone lymphocytapheresis at any time during their participation in the screening protocol and an adequate sample is already available, this may replace the baseline lymphocytapheresis at the discretion of the Principle Investigator. This procedure may last up to 2.5 hours. If the participant is unable to undergo lymphocytapheresis for any reason, 120 cc of whole blood in a heparinized syringe will be collected in its place. The collected mononuclear cells (up to 4×10^9) will be used for immunological studies.
 7. Skin biopsy (research): the punch skin biopsy will be collected once during baseline period. Skin biopsy will be used for isolation, expansion and cryopreservation of fibroblasts for future studies. Specifically, the fibroblast will be transformed to induced pluripotent stem cells (iPS), which can then be differentiated into neurons and glial cells. The purpose of these future studies is to evaluate if neurons from PP-MS patients are more susceptible to oxidative damage than neurons from other forms of MS (RR-MS and SP-MS) and neurons derived from patients with other disorders (i.e. controls). These future studies will be performed only after sufficient number of control samples of fibroblasts are collected/banked under alternative NIB protocols.

7.5.7 Drug administration

We requested a new investigational new drug (IND) number from Food and Drug Administration (FDA) on 3/9/09. A copy of this protocol has been submitted to the FDA for review.

Idebenone (150mg tablets) or placebo will be administered orally as five tablets, three times per day with food. Patients will receive a 6 month supply of the study medication. Patients will record drug administration in a drug diary to monitor compliance. Remaining pills and bottles will be counted during clinic visits every 6 months to assess overall drug compliance.

Idebenone is a short-chain benzoquinone derivative of similar structure to ubiquinone (coenzyme Q₁₀). This compound was synthesized and developed initially by Takeda Chemical Industries, Ltd. (Osaka, Japan) and designated as CV-2619. The chemical name for idebenone is 6-(10-Hydroxydecyl)-2,3-dimethoxy-5-methyl-1,4-benzoquinone. Santhera Pharmaceuticals (Switzerland) Ltd, will supply the drug for this study as specified by a clinical trial agreement (Appendix H). Idebenone is formulated as film-coated 150 mg tablets. For list of inactive ingredients see section 4.5.4.

Idebenone with a certificate documenting analytical results, release of the product for the clinical study and shelf life will be provided to the NINDS by Santhera Pharmaceuticals (Switzerland) Ltd. Idebenone tablets and matching placebo are supplied in high density polyethylene (HDPE) bottles, stored at room temperature (15-25°C) and must be protected from direct sunlight. Temperature excursions are permitted as follows: up to 30°C for 12 months, up to 40°C for 6 months.

7.5.8 Records

The NINDS/Clinical center record will be used for trial-related documentation. Specific trial-related pages will include:

1. Inclusion and exclusion criteria checklist
2. Documentation of the history and physical examination (using structured NIB progress note).
3. A copy of the written informed consent.
4. A record of all research tests, scores, and results.
5. Documentation of all clinical laboratory results.
6. Documentation of any concomitant medications taken by the patient.
7. A record of any and all adverse events experienced during the study.

7.5.9 Storage of data and samples

All collected samples, including serum, blood, CSF, expanded fibroblasts and peripheral blood mononuclear cells (PBMC) derived from aphereses, will be coded and stored in secured freezers on the NIH campus. All patients enrolled in this protocol will be assigned a sequential code and all biological samples collected for this patient will be labeled with patient's code, type of the sample, volume, number of cells (if indicated) and date of freezing.

The intent is for all samples to be analyzed in laboratories on the NIH campus. As new relevant methodologies are developed, however, there is a conceivable future interest to process samples off-site in a collaborating laboratory. Patients will be made aware of this possibility at the time of enrollment and will be asked to consent to potential off-site processing. In this event, IRB approval from NIH and from the collaborating institution will be obtained, and materials will be shipped in accordance with NIH and federal regulations.

7.6 Follow-up/termination procedures

7.6.10 Trial termination procedures

The individual participation in the trial will end with the last trial visit at month 24. There will be a telephone interview 1 month after completion of the trial to verify that there has been no worsening of the clinical symptoms. In case of serious adverse events ongoing at the last trial visit (month 24) **or** of SAEs newly reported during the telephone contact, the patient will be invited to undergo a full examination and assessment at the study site. Additionally, patients will be asked to report any serious adverse event that may occur after this last interview, if they perceive them as possibly related to the participation in this study. The trial will be officially terminated after all enrolled subjects complete the last scheduled visit (month 24) or withdraw from the trial. The trial may be terminated prematurely by the DSMB if there is a concern about safety of idebenone in PP-MS patients. Because no interim analysis requiring unblinding of patient allocation is planned, there will be no termination of the trial based on therapeutic futility.

As of this protocol amendment, data analysis has been completed and demonstrated that idebenone, while being safe and well-tolerated, had no significant efficacy on either primary or any secondary outcome measures, in comparison to placebo. Data and samples from this study will be transferred into protocol 09-N-0032 for continued analysis. Participants will be formally informed of the study results by a written letter (uploaded to PTMS).

All clinical data will be prospectively acquired and entered into the NIB research database. Similarly, all neuroimaging volumetric data will be transcribed into the NIB research database. All immunological and/or biomarker data will be logged and stored in a separate research database on the NINDS server. In order to limit inter-assay variability, for those biomarkers that can be assessed from cryopreserved biological samples, all time-points for individual research subjects will be run in parallel. All databases will be locked upon the last entry of data from the last patient who completes the trial.

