5.2 Goals of the study

The primary goals are:

1. To determine the safety of long-term (24 months) idebenone therapy at 2250 mg/day in patients with PP-MS.
2. To determine the efficacy of idebenone versus placebo in inhibiting individualized rates of CNS tissue destruction as measured by clinical biomarkers and quantitative imaging biomarker of brain atrophy (i.e. ventricular volume)

The secondary goals are:

1. To investigate the mechanism of action of idebenone in PP-MS.
2. To determine/define biomarkers of mitochondrial dysfunction and oxidative damage in PP-MS patients.
3. To define biomarkers indicative of therapeutic effect of idebenone on mitochondrial dysfunction and on limiting oxidative damage in PP-MS patients.
4. To collect longitudinal data in the placebo arm that will allow us to evaluate whether the assumptions on which we based our primary analysis (i.e. that the CNS tissue destruction is intra-individually linear, but inter-individually different within 3 year time period) are

correct or not. This will allow us to calculate more precise sample size/power calculations for future neuroprotective trials in PP-MS.

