3.3 Statistical hypothesis

The primary goal of this study is to determine the safety of long-term (24 months) idebenone therapy at 2250 mg/day in patients with PP-MS.

The primary efficacy objective of this final analysis of the IPPoMS study is to investigate the effect of idebenone compared with placebo on the disability progression using the CombiWISE score with the following statistical hypotheses:

H_0 : There is no difference between idebenone and placebo in the disability progression during the 2-year treatment period.

H_A : The disability progression in idebenone-treated patients is slower than in the placebo-treated patients during the 2-year treatment period.

In addition to the difference between the treatment groups, the within-group changes in each treatment group will be evaluated by comparing the disability progression during the pre-treatment period to the progression during the treatment period.

4 Endpoints

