4.1 Primary safety endpoints

The primary safety endpoints include premature discontinuations of study treatment, serious adverse events and all adverse events. For more details on the analysis of the safety data, see Section 12 of this SAP.

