14.1 Disposition

Number of enrolled, randomized, completed and discontinued patients will be summarized. In addition, the reasons for discontinuations will be tabulated. The time to premature discontinuation will be illustrated with Kaplan-Maier plots.

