14.2 Adverse events

All Adverse Events (AEs) will be coded using the Medical Dictionary for Regulatory Activities (MedDRA). The treatment-emergent AEs (i.e., events which start or worsen during the study treatment) will be tabulated by treatment group (when applicable), system organ class and preferred term. Both subject counts (number of patients reporting the event at least once) and event counts (total number of reported events) will be calculated. The percentages out of all patients will be calculated for the subject counts. In addition, incidence rates will be calculated by dividing the event count by patient years of exposure to the study treatment (double-blind phase) or by duration of follow-up (pre-treatment baseline phase).

In addition, the treatment-emergent AEs will be evaluated by severity grade and by relationship to the study treatment. The serious AEs will also be summarized.

15 Execution of statistical analyses

NINDS will be responsible for the final statistical analyses. Santhera Pharmaceuticals may support in conduction of the analyses, but in this case analyses have to be approved by the NINDS.

16 Changes in the planned analyses

This SAP defines the analyses planned in the protocol in more detail and introduces additional sensitivity analyses of the primary endpoint. In addition, the analyses of the secondary efficacy endpoints and safety data have been defined in more detail.

The following minor change was done for the analysis of the primary endpoint. The AUC values will be scaled to the duration of the assessment period, instead of using the calculated AUC values as such (and by dividing the double-blind period AUC values by 4). This change was done prior to unblinding of the study and was deemed as minor and not requiring a protocol amendment.

17 Hardware and software

Statistical analysis, tables and patient data listings will be performed with SAS[®] version 9.4 for Windows (SAS Institute Inc., Cary, NC, USA).

18 References

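### Safety is the first primary goal, but the SAP plans no between-arm estimate or interval for it, so the protocol's unqualified statement that safety was demonstrated goes beyond what the planned analysis at about 33 per arm can support

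*Protocol*

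**What the plan says.** Protocol 5.2 lists as its first primary goal "To determine the safety of long-term (24 months) idebenone therapy at 2250 mg/day in patients with PP-MS". SAP 3.3 goes further: "The primary goal of this study is to determine the safety of long-term (24 months) idebenone therapy at 2250 mg/day in patients with PP-MS". The null and alternative hypotheses that follow it concern efficacy only.

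SAP 4.1 defines the endpoints: "The primary safety endpoints include premature discontinuations of study treatment, serious adverse events and all adverse events". Their planned analysis is in SAP 14:

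- Adverse events (14.2): "Both subject counts (number of patients reporting the event at least once) and event counts (total number of reported events) will be calculated". Then: "The percentages out of all patients will be calculated for the subject counts". Incidence rates per patient-year of exposure, tables by severity grade and by relationship to treatment, and a summary of serious events are also planned.
- Discontinuation (14.1): counts, tabulated reasons, and "The time to premature discontinuation will be illustrated with Kaplan-Maier plots".
- Both phases are covered. The untreated pre-treatment year is summarised as well as the double-blind phase.

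No between-arm difference or ratio, interval, acceptable rate, margin or upper bound is attached to any safety endpoint. SAP 9 says that confidence intervals are two-sided, but does not assign one to safety. The protocol section on criteria for stopping the study leaves the matter to the DSMB, with no numerical boundary.

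Protocol 7.6.10, in text written after the analysis, states that "data analysis has been completed and demonstrated that idebenone, while being safe and well-tolerated, had no significant efficacy".

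**The concern.** The two halves of the Protocol 7.6.10 sentence are worded differently. Efficacy is reported as a non-significant result; safety is reported as something shown. The plan sets no criterion by which safety could be shown and produces no figure for how large an excess over placebo remains compatible with the data. Two arms of about 33 can look alike while a clinically relevant excess of serious events or discontinuations is still possible.

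At stake is what the trial can say on its first primary goal. Earlier experience does not fully fill the gap: Protocol 8.1 says that, to the authors' knowledge, idebenone had not been given to patients with presumed immune-mediated disorders, and that its effect on their immune responses was hard to predict. Protocol 7.6.10 also says that participants will be told the results by letter.

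**Working it through.** **Inputs.** 33 per arm (Protocol 6.1, SAP 6.2); two-sided 5% (SAP 9, general rule). The documents give no design rate for any safety endpoint, so 10% is an assumption. Protocol 9.1.15 cites earlier-trial rates for individual events of 3.0% to 8.9%.

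**The plan's own figures.** There is no safety power or precision figure to reproduce. The 33 per arm is read from a published brain-atrophy table (SAP 6.1). It is consistent with that table's own scaling: 92/33 = 2.79, against (50/30)² = 2.78. The later CombiWISE table also reproduces as a paired t-test (28 pairs, difference 25.62, SD of the difference 46.2 × √(2 × (1 − 0.5)) = 46.2: power 0.8075, stated 0.807). Both are efficacy calculations and say nothing about safety.

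**1. Identical counts, 3/33 in each arm.** Wilson 95% limits for one arm, with p = 3/33 = 0.0909 and z = 1.96:

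- centre = (p + z²/2n)/(1 + z²/n) = (0.0909 + 0.0582)/1.1164 = 0.1336
- half-width = z√(p(1−p)/n + z²/4n²)/(1 + z²/n) = 1.96 × √(0.002504 + 0.000882)/1.1164 = 0.1022
- limits 0.0314 and 0.2357

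Newcombe upper limit for the difference = 0 + √((0.2357 − 0.0909)² + (0.0909 − 0.0314)²) = √(0.02097 + 0.00354) = 0.157. An observed difference of zero therefore leaves up to about +16 percentage points.

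**2. No events in 33 treated patients.** One-sided 95% upper bound = 1 − 0.05^(1/33) = 0.087, or 8.7%.

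**3. Chance of missing a true excess, if a test were used.** I summed the product of two binomial probabilities (n per arm) over all outcomes with two-sided p ≥ 0.05:

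| n per arm | placebo vs idebenone | missed, chi-square | missed, Fisher exact |
|---|---|---|---|
| 33 | 10% vs 20% | 79% | 88% |
| 40 | 10% vs 20% | 75% | 84% |
| 33 | 8.9% vs 17.8% | 81% | 91% |
| 33 | 10% vs 30% | 45% | 58% |

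The third row doubles the highest earlier-trial rate in Protocol 9.1.15, so the result does not hang on the assumed 10%. By the normal approximation, 80% power for 10% versus 20% would need 199 per arm.

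**Sensitivity to arm size.** The Safety population is everyone with at least one dose (SAP 8), and 33 per arm is the target after 20% drop-out, so the arms may be somewhat larger. Protocol 11.5 describes pre-treatment cohorts of 35 + 34 = 69 patients, and Protocol 7.4 mentions drug supply for 40. At 40 per arm, 0/40 still leaves 1 − 0.05^(1/40) = 7.2%, and the miss rates in the table fall only slightly.

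**The case against.** Descriptive safety reporting is usual in a Phase I/II trial of this size, and SAP 9 calls the study exploratory. No safety test is planned, so miss rates do not describe the planned review. Both points stand: the miss rates are illustrations of precision, and a powered safety test is not what is missing.

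A reader might infer from Protocol 7.6.10 that the sponsor declared the safety goal met, and that the conclusion can rest only on seeing no difference between the arms. The documents do not support either inference. The sentence does not mention the goal or say how the safety conclusion was reached. The plan offers other bases: event rates in the untreated year, severity, judged relationship, reasons for discontinuation, scheduled laboratory monitoring and DSMB review. These are real sources of safety information, but none of them bounds the excess over placebo.

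A reader might also infer that the completed analysis contained no interval. That cannot be known. The study report and the participant letter are not among the documents, so the absence is shown for the plan only.

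Finally, changing a pre-unblinding SAP after the analysis would be post hoc. That is correct, and it determines where the fix belongs.

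**Conclusion.** The point holds as a mismatch between the plan and the wording of one conclusion. The plan gives the first primary goal no between-arm estimate and no measure of uncertainty, while Protocol 7.6.10 states safety and tolerability as demonstrated, without qualification. At about 33 per arm the data could look reassuring and still be compatible with an excess of about 16 percentage points (3/33 in each arm), or with a true rate of up to 8.7% for an event never seen on idebenone.

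These sizes rest on 33 per arm and on illustrative counts and rates; at 40 per arm the picture is much the same. Nothing here suggests that idebenone was unsafe, and the efficacy result is not affected. The change is a worthwhile, cheap improvement: it alters what the trial can claim on its first primary goal.

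**What to change.** Because the analysis is complete, add the following to the study report as a documented addition to SAP 14:

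- For premature discontinuation, any serious adverse event and any adverse event: the idebenone-minus-placebo difference in proportions with a 95% Newcombe interval.
- For the event counts: the incidence-rate ratio with a 95% interval.
- For serious events not seen on idebenone: the exact upper bound, using the actual number treated.

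Reword the safety part of the Protocol 7.6.10 sentence, and any results letter that repeats it. If it is the case, say that no excess over placebo was observed; give the upper 95% limit for the excess; and state that smaller or rarer harms are not excluded.

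Cost: a few lines of code on data already tabulated and a wording change, with no new patients or data. The downside is a less favourable safety statement with wide intervals.
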